4.2 Study rationale

Given that extension of fields with chronic actinic sun damage can exceed the usually treated area size of 20-25 cm² (23), particularly when also taking AK in the periphery into consideration, safe and efficient options for the treatment of these expanded AK areas are needed.

FDA-approved treatment options for field-directed AK treatment comprise formulations containing ingenol mebutate or diclofenac/hyaluronic acid (3 %/2.5 %), most of which require repeated applications for up to several months or lead to side effects related to cytotoxic and/or inflammatory reactions induced by the treatment that may last for the entire treatment period or even longer.

Compared with other methods like surgery, abrasion, cryotherapy, and alternative topical treatments, use of PDT is advantageous especially due to the high selectivity of the treatment, but also based on the short treatment period that can be entirely controlled by the physician,

and the excellent cosmetic results (24). In addition, a European network meta-analysis of the relative clinical efficacy of 10 different treatment modalities for mild to moderate AK on the face and scalp, including PDT products as well as formulations containing cryotherapy, 5-fluorouracil, imiquimod, ingenol mebutate or diclofenac/ hyaluronic acid, has shown that ALA PDT using BF-200 ALA was the most efficacious treatment option (25).

Today, besides Ameluz[®], one further PDT product containing ALA is available in the US market. Levulan[®] Kerastick[®] contains ALA at a concentration of 20 % and is provided as a 2-component system. Consequently, ALA has to be dissolved immediately before use. By label, use of Levulan[®] Kerastick[®] is restricted to lesion-directed treatment of minimally to moderately thick AKs located on the face and scalp as well as on upper extremities. Thus, Ameluz[®] is the only PDT product available in the US market which has been approved for the field-directed treatment of AKs.

So far, availability of clinical data for the treatment of large AK areas is limited. However, several studies for treatment of AK areas >20 cm² using ALA PDT have indicated good efficacy and tolerability (26–29). Therefore, PDT may represent an adequate option for the treatment of extended cancerous fields preventing long treatment duration with sequential treatment sessions.

For these reasons, this exploratory study aims at obtaining pharmacokinetic profiles of ALA and its metabolite PpIX after a single PDT treatment with BF-200 ALA in subjects with actinic keratosis in an expanded treatment field of 60 cm² located on the face/scalp or in the periphery, applying approx. 458 mg ALA in total (7.8 mg ALA/cm²). In addition, subjects' safety/tolerability during and after treatment will be assessed.

4.3 Risk/benefit analysis

This open-label Phase I study will include diseased subjects presenting with at least 12 AK lesions with diameter of ≥ 4 mm within the 60 cm² treatment field. All participants will receive active BF-200 ALA treatment - already marketed for the treatment of AK in the US, EU, Switzerland and Israel under the brand name Ameluz[®] - in combination with conventional red-light PDT illumination.

Clinical efficacy and safety of BF-200 ALA in combination with conventional red-light PDT illumination for the treatment of mild to moderate AK on the face and scalp were previously examined in one dose-finding study, and three confirmatory studies encompassing a total of 885 randomized subjects comprising 462 subjects (2674 lesions) exposed to BF-200 ALA (7.8% ALA) (30–32). Additionally, one confirmatory intra-individual study (ALA-AK-CT010) with 50 subjects was performed for the assessment of clinical efficacy and safety of BF-200 ALA for the treatment of AKs located on extremities or trunk/neck. In these pivotal clinical trials, complete clearance of subjects 12 weeks after the first PDT with BF-200 ALA was shown to be up to 61.8 % and total lesion clearance was up to 84.2 % (30–32). Thus, we expect that a comparable percentage of participating subjects will benefit from the single PDT treatment which will be administered in the current study.

In previous clinical trials with BF-200 ALA, local application site reactions were observed in 84-100 % of the subjects. These reactions are expected, given the therapeutic principle of PDT, which is based on phototoxic effects. The most common signs and symptoms were application site erythema, pain/burning, irritation, and edema. Most adverse reactions

occurred during illumination or shortly afterwards. Symptoms were usually of mild or moderate intensity (investigator's assessment on a 4-point scale) and lasted for 1 to 4 days in most cases; however, in some cases, they persisted for 1 to 2 weeks or even longer. It is known that the intensity of AEs depends on the type of illumination used for PDT and correlates with the higher clearance rate achieved by the use of narrow spectrum lamps, e.g. BF-RhodoLED®. In rare cases, adverse reactions may require interruption or discontinuation of the illumination.

Common adverse effects of PDT with BF-200 ALA include headache and reactions at the application site, such as abnormal sensation, increased sensitivity to pain, discomfort, erosion, and discharge. More detailed information on known adverse reactions is provided in the prescribing information (PI) for Ameluz® (19). This drug is contraindicated in subjects with known hypersensitivity to ALA, to porphyrins or to any excipients of Ameluz®, and in subjects with porphyria or photodermatoses.

It is assumed that local adverse reactions in more extended treatment fields will be similar to those known from treatment of AK lesions as well as cancerous fields described previously. Nonetheless, an appropriate form of pain management has to be considered as PDT pain may be related to the size of the treatment field(s) (33). For this reason, pain management will be performed according to established guidelines (34,35) but restrictions for co-medication described in this protocol must be taken into consideration.

In this study, inclusion and exclusion criteria have been chosen to minimize possible risks due to the administration of BF-200 ALA, and to ensure a uniform study population. BF-200 ALA and the PDT lamp BF-RhodoLED® will be handled by appropriately trained study personnel. For maximal comparability to previous studies, up to two BF-RhodoLED® lamps will be used simultaneously, such that the light dose of 37 J/cm^2 will be applied to the entire 60 cm^2 treatment field in 10 min.

5 STUDY OBJECTIVES

5.1 Primary objectives

The primary objectives of the study are:

- Assessment of baseline-adjusted plasma concentration-time curves for ALA after a single PDT treatment applying 3 tubes of BF-200 ALA in conjunction with the BF-RhodoLED® under maximal use conditions in subjects with mild to severe actinic keratosis.
- Assessment of baseline-adjusted plasma concentration-time curves for PpIX after a single PDT treatment applying 3 tubes of BF-200 ALA in conjunction with the BF-RhodoLED® under maximal use conditions in subjects with mild to severe actinic keratosis.

Data will be analyzed overall and according to strata (treatment area: face/scalp or periphery (neck/trunk/extremities)).

5.2 Secondary objectives

The secondary objective of this study is to calculate pharmacokinetic parameters based on baseline-adjusted plasma concentration data of ALA and PpIX (if data permits) and to evaluate the safety and tolerability of PDT with BF-200 ALA under maximal use conditions.

Pharmacokinetics:

The secondary objectives of the study regarding pharmacokinetics include:

- Evaluation of baseline-adjusted pharmacokinetic parameters of ALA.
- Evaluation of baseline-adjusted pharmacokinetic parameters of PpIX.

Safety:

The secondary objectives of the study regarding safety include:

- Assessment of safety and tolerability of PDT with BF-200 ALA under maximal use conditions

All secondary parameters will be analyzed descriptively and in an exploratory way overall and according to strata.

5.3 Tertiary objectives

To compensate for situations in which baseline-adjustment mathematically impairs calculation of PK parameters, the tertiary objective of this study is to calculate unadjusted PK parameters of ALA and PpIX as well.

The tertiary objectives include:

- Evaluation of unadjusted plasma concentration-time curve for ALA and evaluation of unadjusted pharmacokinetic parameters of ALA.
- Evaluation of unadjusted plasma concentration-time curve for PpIX and evaluation of unadjusted pharmacokinetic parameters of PpIX.

All tertiary parameters will be analyzed descriptively and in an exploratory way overall and according to strata.

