14.1 Analysis variables

The primary endpoints for pharmacokinetics are the

- Baseline-adjusted plasma concentrations of ALA for obtaining baseline-adjusted plasma concentration-time curves
- Baseline-adjusted plasma concentrations of PpIX for obtaining baseline-adjusted plasma concentration-time curves

Secondary endpoints are the

- Baseline-adjusted AUC_{0-t} , baseline-adjusted $AUC_{0-\infty}$, baseline-adjusted C_{max} , T_{max} , $T_{1/2}$, and λ_Z for ALA (if data permit)
- Baseline-adjusted AUC_{0-t} , baseline-adjusted $AUC_{0-\infty}$, baseline-adjusted C_{max} , T_{max} , $T_{1/2}$, and λ_Z for PpIX (if data permit)
- Assessment of safety and tolerability of PDT with BF-200 ALA under maximal use conditions, including:
 - Frequency and severity of treatment-emergent adverse events (TEAEs), including serious adverse events (SAEs). TEAEs are defined as all AEs with onset or worsening after treatment with the investigational medicinal product and device.
 - Overall tolerability.
 - Application site skin reactions in the treatment field(s) during and post PDT.
 - Application site discomfort during and after illumination reported by the subjects.
 - Application site pain during PDT on an 11-point Numeric Rating Scale (NRS-11).
 - Vital signs data.
 - Safety laboratory data if clinically significant deviations occur.
 - Data from the physical examinations if clinically significant findings occur.

Tertiary endpoints are the

- Unadjusted plasma concentration-time curve for ALA and pharmacokinetic parameters of ALA: unadjusted AUC_{0-t} , unadjusted $AUC_{0-\infty}$, unadjusted C_{max} , T_{max} , $T_{1/2}$, and λ_Z if data permit

- Unadjusted plasma concentration-time curve for PpIX and pharmacokinetic parameters of PpIX: unadjusted AUC_{0-t} , unadjusted $AUC_{0-\infty}$, unadjusted C_{max} , T_{max} , $T_{1/2}$, and λ_z if data permit

All pharmacokinetic characteristics (AUC_{0-t} , $AUC_{0-\infty}$, $T_{1/2}$ and λ_z) will be derived from baseline-adjusted as well as unadjusted plasma concentrations of ALA and PpIX as described above.

The pharmacokinetic parameters for ALA and PpIX will be derived from plasma using noncompartmental methods and are listed in Table 6. Values < LLOQ and negative values after baseline adjustment are set to zero and disregarded when displaying data on a logarithmic scale.

Table 6: List of pharmacokinetic parameters

Parameter	Description
C_{max}	Observed maximum baseline-adjusted or unadjusted plasma concentration

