2.3 Tertiary Endpoints

- Unadjusted plasma concentration-time curve for ALA
- Unadjusted plasma concentration-time curve for PpIX
- Pharmacokinetic parameters of ALA: unadjusted AUC_{0-t} , unadjusted $AUC_{0-\infty}$, unadjusted C_{max} , T_{max} , $T_{1/2}$, and λ_z
- Pharmacokinetic parameters of PpIX: unadjusted AUC_{0-t} , unadjusted $AUC_{0-\infty}$, unadjusted C_{max} , T_{max} , $T_{1/2}$, and λ_z

The analysis of the tertiary endpoints is described in a separate pharmacokinetics SAP.

3 Analysis Sets

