3. STUDY OBJECTIVES AND ENDPOINTS

Primary objectives

- Assessment of baseline-adjusted plasma concentration-time curve for ALA after a single PDT treatment applying 3 tubes of BF-200 ALA under maximal use conditions in subjects with actinic keratosis.
- Assessment of baseline-adjusted plasma concentration-time curve for PpIX after a single PDT treatment applying 3 tubes of BF-200 ALA under maximal use conditions in subjects with actinic keratosis.

Secondary objectives

- Evaluation of pharmacokinetic parameters of ALA: baseline-adjusted AUC_{0-t} , baseline-adjusted $AUC_{0-\infty}$, baseline-adjusted C_{max} , T_{max} , $T_{1/2}$, and λ_Z if data permit
- Evaluation of pharmacokinetic parameters of PpIX: baseline-adjusted AUC_{0-t} , baseline-adjusted $AUC_{0-\infty}$, baseline-adjusted C_{max} , T_{max} , $T_{1/2}$, and λ_Z if data permit
- Assessment of safety and tolerability of PDT with BF-200 ALA under maximal use conditions (not part of this SAP)

Tertiary objectives

- Assessment of unadjusted plasma concentration-time curve for ALA and evaluation of pharmacokinetic parameters of ALA: unadjusted AUC_{0-t} , unadjusted $AUC_{0-\infty}$, unadjusted C_{max} , T_{max} , $T_{1/2}$, and λ_Z if data permit
- Assessment of unadjusted plasma concentration-time curve for PpIX and evaluation of pharmacokinetic parameters of PpIX: unadjusted AUC_{0-t} , unadjusted $AUC_{0-\infty}$, unadjusted C_{max} , T_{max} , $T_{1/2}$, and λ_Z if data permit

Data will be analyzed overall and according to strata (treatment area: face/scalp or periphery (neck/trunk/extremities)).

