10. PHARMACOKINETIC PARAMETERS

The pharmacokinetic parameters for ALA and PpIX which will be derived from plasma using non-compartmental methods are listed in the table below. Values < LLOQ and negative values after baseline-adjustment will be set to zero for calculation of PK parameters. The mean of the three pre-dose samples (Visit 1, -0.5 h and 0 h predose at Visit 2) will be used for baseline adjustment.

Parameter	Description
C_{\max}	Observed maximum baseline-adjusted or unadjusted plasma concentration
AUC_{0-t}	Area under the baseline-adjusted as well as unadjusted plasma concentration-time curve from time zero to the last sampling time point at which the concentration was at or above lower limit of quantification (LLOQ); $t(\text{last})$ is defined as the last value > 0 after baseline adjustment. AUC_{0-t} will be calculated according to the linear trapezoidal formula
$AUC_{0-\infty}$	Area under the baseline-adjusted as well as unadjusted plasma concentration-time data extrapolated to infinity $(AUC_{0-\infty} = AUC_{0-t} + C_t/\lambda_z)$
$\%AUC_{t-\infty}$	Proportion of extrapolated part ($\%AUC_{t-\infty}$) $(1 - [AUC_{0-t}/AUC_{0-\infty}]) \cdot 100$
t_{\max}	time to reach C_{\max}
$t_{1/2,\lambda_z}$	apparent terminal half-life, calculated by $\ln 2/\lambda_z$
λ_z	Terminal rate constant, assuming first order elimination kinetics: $C(t) = \beta * \exp(-\lambda_z t)$. λ_z denotes the terminal rate constant estimated by linear regression analysis from a range of concentrations in the terminal phase estimated for each treatment and subject by log-linear regression from the linear portion of the logarithmic transformed concentration-time plot. The algorithm will start with the last 3 points with quantifiable concentrations and increases the number of involved points by 1 until the time point after C_{\max} restricted on time points after removing of the BF-200 ALA gel (all PK samples after the gel is wiped off [after 3h±10 min]). For each regression an adjusted R^2 will be computed: $\text{Adjusted } R^2 = 1 - \frac{(1 - R^2) \cdot (n - 1)}{n - 2},$ where n denotes the number of data points ($n \geq 3$). The regression with the largest adjusted $R^2 > 0.8$ will be selected for the estimation of λ_z using WinNonlin option "BestFit".

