The pre-dose sample always will be considered as if it had been taken simultaneously with the application of BF-200 ALA. If there should have been any deviations in post-dose sampling, the actual sampling times relative to preceding drug administration will be used unless stated otherwise. Missing data will not be replaced or imputed in any way.

AUC_{0-t} and $AUC_{0-\infty}$ will be regarded as unreliable if more than three consecutive results are missing or if the concentrations were quantifiable for fewer than 5 time points.

C_{\max} and t_{\max} will be regarded as unreliable if the maximum was observed preceding or following a sample with missing data. In case of multiple peaks, C_{\max} and t_{\max} refer to the highest measured concentration even if there should be earlier peaks. In case of two or more samples with the same concentration (as supplied by the analyst), t_{\max} refers to the earlier of these.

Concentrations for PK analyses will be used as supplied by the analytical laboratory.

The calculation of λ_z will be considered unreliable in case of $r^2 < 0.8$. The starting time (T_k) for calculation of λ_z and the number of data points in the regression (N_z) as well as the coefficient of determination r^2 will also be tabulated.

λ_z , $t_{1/2}$, $AUC_{0-\infty}$ will only be determined in subjects in which the log-linear terminal phase can clearly be defined. The value of $AUC_{0-\infty}$ will be considered unreliable but will be reported if the terminal area beyond the last quantified sample is greater than 20% of the total $AUC_{0-\infty}$.

If any pharmacokinetic parameter should be classified as unreliable, all calculations that use this parameter will be considered missing.

Unreliable parameters will be listed and flagged accordingly and set to missing for calculation of descriptive statistics and statistical analysis.

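### Half-life, λz and AUC0-∞ of endogenous ALA and PpIX should not be derived from unadjusted concentrations with a model that decays to zero

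*Protocol*

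**What the plan says.** Protocol 5.3 explains why unadjusted parameters exist. They are meant for situations in which adjustment gets in the way: "baseline-adjustment mathematically impairs calculation of PK parameters, the tertiary objective of this study is to calculate unadjusted PK parameters". Protocol 14.1 then says that the AUCs, T1/2 and λz "will be derived from baseline-adjusted as well as unadjusted plasma concentrations of ALA and PpIX as described above". The endpoint lists agree: the main (safety) SAP, section 2.3, has "Pharmacokinetic parameters of ALA: unadjusted" AUCs, Cmax, Tmax, T1/2 and λz, and the PK SAP, section 3, has "Assessment of unadjusted plasma concentration-time curve for ALA and evaluation of pharmacokinetic parameters of ALA: unadjusted" versions of the same list. Both lists repeat this for PpIX.

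The definitions in Protocol Table 6 and PK SAP section 10 are shared between the two kinds of data. AUC0-∞ is the "Area under the baseline-adjusted as well as unadjusted plasma concentration-time data extrapolated to infinity", computed as AUC0-t + Ct/λz. λz is the "Terminal rate constant, assuming first order elimination kinetics", with C(t) = β·exp(−λz·t), and T1/2 = ln2/λz.

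PK SAP section 10 limits what is reported in three ways:

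- The chosen regression needs an adjusted R² above 0.8.
- λz, T1/2 and AUC0-∞ "will only be determined in subjects in which the log-linear terminal phase can clearly be defined".
- AUC0-∞ "will be considered unreliable but will be reported if the terminal area beyond the last quantified sample is greater than 20% of the total" area. Unreliable values are listed and flagged but set to missing in the summaries.

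Protocol 4.1 describes ALA as an endogenous metabolite and says that ALA and PpIX have naturally occurring levels before dosing. With one tube, it reports no rise in PpIX and a slight, transient rise in ALA.

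**The concern.** An unadjusted profile of an endogenous substance falls towards its baseline, not towards zero. Fitting an exponential that decays to zero mixes the elimination of absorbed drug with the flat endogenous level. The slope is too shallow and the half-life too long. The extrapolated tail Ct/λz then assigns a finite value to an area that is infinite.

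The bias is largest when the rise over baseline is small. That is also where baseline adjustment is most likely to fail, so the fallback is weakest in the situation for which Protocol 5.3 offers it. An unadjusted half-life would be summarised alongside the adjusted one although it partly reflects the endogenous level.

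**Working it through.** **Inputs from the documents.** Samples after gel removal are at 3.5, 4, 5, 6, 8 and 10 h (Protocol Table 1). The fitting rule starts with the last three points and adds one at a time back to the point after Cmax, using only times after gel removal. The fit with the largest adjusted R² is kept if that exceeds 0.8 (PK SAP section 10). AUC uses the linear trapezoid. The plan gives no figure for the quantities in question, so there is none to reproduce.

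**Assumed inputs.** Baseline B is constant and set to 1. E/B is the excess at 3 h over baseline, from 0.5 to 20. The true half-life runs from 0.5 to 3 h. The profile rises linearly from B at 0 h to B + E at 3 h.

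**Direction.** After 3 h, C(t) = B + E·exp(−k(t−3)). The log slope is −k × [E·exp(−k(t−3))] / [B + E·exp(−k(t−3))]. For B > 0 the fraction is below 1 at every time, so the slope is always shallower than −k. The integral of B to infinity diverges. Neither result depends on the assumed values.

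**Worked case: E/B = 5, true T1/2 = 1 h (k = 0.693).** Concentrations at the six times are 4.54, 3.50, 2.25, 1.63, 1.16 and 1.04.

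- The rule selects all six points: λz = 0.2245, adjusted R² = 0.86, accepted. T1/2 = 0.693/0.2245 = 3.09 h, against a true 1 h.
- AUC0-10 = 24.93. The tail is 1.039/0.2245 = 4.63. AUC0-∞ = 29.56, with 4.63/29.56 = 15.7% extrapolated, so it passes the 20% rule.
- Adjusted: AUC0-10 = 24.93 − 10 = 14.93. The tail is 0.039/0.693 = 0.06. AUC0-∞ is about 15.0 and T1/2 = 1.00 h.

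**Noise-free grid: fitted divided by true T1/2** (rej. = rejected by the R² rule)

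| True T1/2 | E/B 0.5 | 1 | 2 | 5 | 10 | 20 |
|---|---|---|---|---|---|---|
| 0.5 h | rej. | rej. | rej. | rej. | rej. | rej. |
| 0.75 h | rej. | rej. | rej. | rej. | 3.1 | 2.3 |
| 1 h | rej. | rej. | 9.3 | 3.1 | 2.2 | 1.7 |
| 1.5 h | 14.7 | 8.0 | 4.6 | 2.5 | 1.6 | 1.3 |
| 2 h | 9.8 | 5.5 | 3.3 | 2.0 | 1.4–1.5 | 1.2 |
| 3 h | 6.5 | 3.8 | 2.4 | 1.6 | 1.3 | 1.13–1.15 |

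Where a range is shown, it depends on how near-tied fits are resolved.

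**20% rule.** Accepted fits at E/B up to 2 extrapolate 38–73%, so their AUC0-∞ leaves the summaries. At E/B 5 the share is 15.7% (T1/2 1 h), 19.0% (1.5 h), 20.9% (2 h) and 28.0% (3 h), so the first two stay in. The rule never removes λz or T1/2, because neither is calculated from AUC0-∞.

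**No absorption.** Flat profiles, 10,000 each at 10, 15 and 20% lognormal noise: 8–9% return an accepted half-life, with a median of about 10–19 h. That is about 0.085 × 32 = 2.7 subjects per analyte.

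**What the fallback adds.** 3,000 profiles per cell, 10% noise, true T1/2 1–3 h, adjusted by the mean of three pre-dose values with negatives set to zero:

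- At E/B 0.5–1 the unadjusted fit is accepted in about 22–58% of subjects and the adjusted fit in 26–55%.
- Subjects with only an unadjusted fit are about 8–12%. Their T1/2 is a median 2.6–12 times too long.
- At E/B 5 or more, such subjects are about 2% or fewer.
- At E/B 1, the median ratio of fitted to true T1/2 is 0.84–1.26 adjusted, against 3.0–10.5 unadjusted. At E/B 0.5 the adjusted ratio is less clean, 0.72–1.52.

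Repeat runs moved single percentages by a few points at most (for example 18–22% at the lower end of unadjusted acceptance, and up to 2.6% for the last group), without changing the pattern.

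**The case against.** The strongest reply is that little hangs on these outputs. They are tertiary and descriptive, the primary and secondary PK endpoints are baseline-adjusted, and no decision uses an unadjusted half-life. The plan also discloses a good deal: the parameters are named as unadjusted, the half-life as apparent, the mean baseline is drawn on the unadjusted graphs, and the start time, number of points and r² are tabulated for each λz. All of this is true. It limits the impact, but it does not give the estimate a meaning.

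Second, the requirement for a clearly defined log-linear terminal phase could not be simulated and may screen out flat profiles. The acceptance rates above are therefore those of automatic fitting and may overstate what is reported. The clause has no stated criterion, however, and many biased fits look straight: every accepted fit at a true T1/2 of 1.5–3 h has an adjusted R² of 0.89 or more.

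Third, the 20% rule largely handles AUC0-∞ when the rise is small. That stands. Leakage into the summaries appears at about five times baseline, and the rise with three tubes is unknown.

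Fourth, values below LLOQ are set to zero, so a subject whose baseline is below LLOQ would show little or none of this bias. That also stands, and the LLOQ is not given.

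Fifth, Protocol 5.3 speaks of PK parameters in general, including Cmax and AUC0-t, for which unadjusted versions are legitimate, and no rule substitutes an unadjusted value for a missing adjusted one. Both points are right, and the fix keeps those parameters.

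Finally, a footnote could replace deletion. It would reduce misreading, but it would leave summary statistics for an area with no finite true value.

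**Conclusion.** The concern holds. For any quantifiable, roughly constant baseline, the unadjusted T1/2 is systematically too long and the unadjusted AUC0-∞ estimates a quantity that does not exist. Under noise, a few single half-life estimates can still fall below the truth.

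The size cannot be fixed from the documents. Over the assumed range, accepted half-lives are from about 1.13 to 15 times too long, worst at small rises. At very short half-lives the R² rule blocks the output, entirely so at 0.5 h. None of the plan's conditions tests for return to baseline.

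The effect is confined to unadjusted λz, T1/2 and AUC0-∞. Unadjusted Cmax, Tmax and AUC over the sampled interval remain interpretable as total levels. This should be corrected, but it does not threaten the primary or secondary results.

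**What to change.** Delete unadjusted λz, T1/2 and AUC0-∞ from the tertiary endpoints in the Protocol outline, Protocol 5.3, 14.1 and Table 6, the main SAP section 2.3, and PK SAP sections 3 and 10. Keep unadjusted concentrations, Cmax, Tmax and AUC over the sampled interval, labelled as total (endogenous plus absorbed). Report λz, T1/2 and AUC0-∞ from baseline-adjusted data only, and as not estimable where no acceptable fit exists. Record the change in PK SAP section 14, which now reads as not applicable.

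The cost is wording in three documents and fewer tables. Some subjects will have no half-life reported. Under the simulation's assumptions, those who would otherwise have had only an unadjusted one are about 8–12% when the rise is 0.5 to 1 times baseline, and about 2% or fewer when it is five times baseline or more.
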